9.2.2.2 Exclusion Criteria

Following exclusion criteria will be used to extract the eligible study population (see also Figure 2):

Cohort A and B:

- Patients with present opioid and non-opioid pain medication prescriptions in 2012 are excluded from analysis (therapy-naïve patients only).
- Cancer patients will be excluded if the cancer diagnosis is accompanied by at least one of the following treatments in the same quarter: radiation therapy or chemotherapy all defined by the codes in Table 9-3. Diagnoses will be assessed via ICD-10 diagnoses during the inclusion period from 1 January 2012 until index treatment and main and secondary hospital diagnoses (i.e. *Haupt- und Nebendiagnosen*) will be taken into account.
- Palliative care, coded by ICD-10 code Z51.5 or OPS code 8-982*, 8-98e*, 8-98h* before index date is excluded
- Opioid substitution treatment with ICD-10 code Z51.83 in the study period is excluded.

Table 9-3: Exclusion criteria for cancer patients

Name	ICD-10 Code	
Malignant neoplasms	C00-C97	
Plus at least one the following in the same quarter		
Name	Code	Type of Code
Palliative care	Z51.5	ICD-10
Chemo therapy	Z51.1	ICD-10
Radiation therapy	Z51.0	ICD-10
Chemo therapy	8-541* 8-542* 8-543* 8-544* 8-546*	OPS Code

Radiation therapy	8-52*	OPS Code
Palliative care	8-982* 8-98e* 8-98h*	OPS Code

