Exclusion criteria: Patients with previous prescription of opioid medication or non-opioid medication between 01.01.2012 and index treatment will be excluded. Patients with cancer treatment, palliative care or opioid substitution after index treatment will be excluded.

Follow-up: Patients' follow-up period include 5 years after start of opioid resp. non-opioid treatment and chronic pain diagnosis between 01.01.2013 and 31.12.2017. Each patient will be censored at death (death date), switching of study group (opioid --> non-opioid or vice versa), 12 months without treatment or followed-up 5 years until last known record for the patient in the German health claims database, latest at 31.12. 2017 (end of latest data cut), whichever happens first.

Variables:

Outcome Variables include death by any course as primary endpoint and hospitalization due to any course, hospitalization with misuse, addiction diagnoses, outpatient diagnosis of misuse or addiction and treatment procedures as secondary endpoints.

Exposure Variables are pain treatments including opioid and non-opioid treatments.

Other Covariates will be collected for assessments over the course of the study: Age and gender (sex: male, female), charlson comorbidity index. Comorbidities, comedications, region will be collected for Propensity Score Matching.

Data Analysis: The main analysis will focus on each of the 2 main cohorts with chronic pain patients as defined at inclusion and:

- with opioid treatment between 01.01.2013 and 31.12.2017 (named cohort A)
- with non-opioid treatment between 01.01.2013 and 31.12.2017 (named cohort B)

To address the group comparisons adequately, a propensity score matching will be conducted. The main analyses will include a multivariate Cox proportional hazards regression. Additional stratified analyzes will be carried out as follows: Subgroup analyses for each following pain conditions will be conducted: headache (R 51*); pain, not elsewhere classified (R52*); persistent somatoform pain disorder (F45.4*); polyneuropathy in diabetes (E10.4*-E14.4 plus G63.3), kyphosis and lordosis (M40), scoliosis (M41), spinal osteochondrosis (M42), other deforming dorsopathies (M43), ankylosing spondylitis (M45), other inflammatory spondylopathies (M46), spondylosis (M47), other spondylopathies (M48), and spondylopathies in diseases classified

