9.1 Study Design

This is a retrospective observational cohort study based on an anonymized German health claims database. This database contains data on around 4 million insured people from 69 German statutory health insurances (SHI). This research database is a complete, longitudinal claims dataset of approx. 7 million individual patients (ca. 10% of the statutory insured population of Germany) between 2012 and 2017. The analyses for this study will be done on a 4 million patients subset that is stratified by age

and gender based on the 2013 population structure of Germany as reported by the German Federal Statistical Office DeStatis.

This study consists of two cohorts: opioid and non-opioid patients. Only patients who started their therapy between 2013 and 2017 and had no therapy in 2012 (therapy naïve patients) will be included in the study.

Exposure time is defined as max. 5 years after the initial prescription for each patient, so that exposure time is max. 60 months per patient.

Exposure time may end before the end of study if patient died, stopped treatment (end of follow-up after 1 year without treatment with opioids / other pain medication), changed treatment group (from opioids to other pain medication or vice versa) or was lost to follow up due to other reasons (e.g. change of insurance), whichever occurs first.

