9.2 Setting and Study Population

The database contains data on around 4 million insured people from 69 German statutory health insurances (SHI). German SHI system comprises of approximately 120 independent health insurance companies. Funds paid by these SHI to any provider of health care (e.g. hospitals, physicians, pharmacies, psychotherapists and physiotherapists) represent almost the complete picture of the total health care costs of individual patients. All health insurance data can be linked to patients' demographics including age and gender. Health care data in the database include:

- Patient demographics:
 - age
 - gender
 - date of death

- region of residence
- insurance status
- date of insurance start and end
- Hospital care:
 - main diagnosis (ICD-10-GM codes) and additional diagnoses
 - procedures and surgeries
 - date of hospital admission
 - reason for admission (e.g. accident, emergency, normal)
 - date of end of hospital stay
 - reason of end of hospital stay (e.g. regular discharge from hospital, death)
 - DRG-Code
 - costs
- Outpatient care:
 - diagnoses (ICD-10-GM codes)
 - quarter in which the diagnosis was documented
 - procedures performed (EBM codes, e.g. laboratory tests, radiology, echocardiography) and date of procedure
 - type of specialist that documented the diagnosis and performed the procedure (e.g. cardiologist, general practitioner)
 - costs
- Pharmaceutical claims:

- drug dispensed (PZN code, which identifies medications at the package level) – this is mapped to ATC codes and DDDs
- quantity dispensed
- day of prescription
- day of dispensing
- type of specialist prescribing the medication (e.g. general practitioner)
- costs of drugs dispensed from the perspective of the statutory health insurance (without individual rebates between insurance and pharmaceutical companies)
- Physical therapy and technical aids:
 - type of therapy (e.g. massage, occupational therapy, walker, wheel chair)
 - quantity prescribed
 - type of care provider
 - start and end date
 - costs
- Sick leave:
 - diagnoses that cause sick leave
 - duration of sick leave
 - start date of sick leave
 - end date of sick leave

- type of specialist that filled out the sick leave form (e.g. general practitioner)
- costs of sick leave

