To note, data are adjusted within the database to Germany's typical age and sex distribution in accordance with the Federal Statistical Office based on the year 2013 (<https://www-genesis.destatis.de/genesis/online>) to foster its overall representativeness in regards to the population in Germany. Privately insured patients in Germany are not included in this database.

All data used are explicitly approved by the involved statutory health insurances for health care research usage according to § 287 or § 75 of the German social security law (SGB V).

Source population of the study are patients covered by the German Health Claims database over 2012-2017 years.

Study population are patients from the source population meeting inclusion (eligibility) criteria (see section 9.2.2).

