9.2.1 Study Period

Due to data protection regulations in Germany, only an extract of maximum 6 years of data coverage could be available for the research purposes: 1st January 2012 to 31st December 2017.

The **baseline period** is defined as the period prior to the date of first diagnosis of diagnoses or first opioid or non-opioid treatment initiation as described in inclusion criteria (Chapter 9.2.2.1). The baseline assessment period endures between January 01, 2012 and first study medication prescription.

Index treatment is defined as the date of first opioid or non-opioid treatment prescription between 1st January 2013 and 31st December 2017.

Exposure time is defined as time between index treatment and December 31, 2017. Considering data availability of a maximum of 6 years and prescription in a required time period of 60 months, exposure time endures maximum five years. Thus, patients can be censored at death (death date in the linked records), last known record for the patient in the German health claims database, switching of treatment groups (from opioid group to non-opioid group or vice versa), 12 months without opioid/non-opioid treatment or 31st December 2017 (end of latest data cut), whichever comes first.

[figure not shown]
The **outcomes** will be assessed between index treatment and 31.12.2017.

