9.2.2 Patient Eligibility

9.2.2.1 Inclusion Criteria

For the purposes of this study, the requested extraction of the database consists of population of patients with chronic non-cancer pain corresponding to the following criteria. Inclusion and exclusion criteria are also provided in Figure 2.

Figure 2: Inclusion and exclusion criteria

Cohort A

- Patients are included in the long-term opioid group if they started an opioid-therapy between 2013 and 2017 and received consecutive prescriptions for opioid medications over a minimum of 3 quarters, over a 60-month period between January 1, 2013, and December 31, 2017. The treatment will be assessed using the ATC codes of opioid treatment N02AA01, N02AA05, N02AB03, N02AE01, N02AX02, N02AX01, N02AX06 (see also Table 9-1) reported in reimbursed medicines to patients.

- Patients are only included if they have been diagnosed in at least three quarters in the study period with one of the following diagnoses: R51, R52*, M00*-M99*, G43*-G44*, G50.0 or G50.1, F45.4*, G62*, or E10.4*-E14.4 plus G63.3. At least one diagnoses must be between 1 January 2012 and index treatment and main and secondary hospital diagnoses (*i.e. Haupt- und Nebendiagnosen*) will be used to include the patients.

Cohort B

- Patients with non-opioid pain medication are included, if they received a medication therapy with anticonvulsants (gabapentin, pregabalin, carbamazepine), antidepressants or non-opioid analgesics (NSAIDs, Metamizole) over a minimum of 3 quarters, over a 60-month period between January 1, 2013, and December 31, 2017. The non-opioid treatment will be assessed using the ATC codes (N03AX12, N03AX16, N03AF01, see also Table 9-1) of treatment reported in reimbursed medicines to patients.
- Patients are only included if they have been diagnosed in at least three quarters in 2012 with one of the following diagnoses: R51, R52*, M00*-M99*, G43*-G44*, G50.0 or G50.1, F45.4*, G62*, or E10.4*-E14.4 plus G63.3. At least one diagnoses must be between 1 January 2012 and index treatment and main and secondary hospital diagnoses (*i.e. Haupt- und Nebendiagnosen*) will be used to include the patients.

All diagnoses that lead to patient inclusion when coded between 01.01.2012 and index treatment and in at least three quarters within the study period are provided in Table 9-2 below.

Table 9-1: List of ATC codes of study opioid and non-opioids

Name	ATC Code
Study opioids	
Morphine	N02AA01
Oxycodone	N02AA05
Fentanyl	N02AB03

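### Therapy-naive status rests on having no 2012 prescriptions, with no requirement to be insured then, so an established opioid user who joins a participating insurer later can enter Cohort A as a new user

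*Protocol*

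**What the plan says.** The protocol intends a new-user comparison. Section 9.1 admits people who start treatment in 2013 to 2017 and "had no therapy in 2012 (therapy naïve patients) will be included in the study". Section 9.2.2.2 turns this into an exclusion for both cohorts: "Patients with present opioid and non-opioid pain medication prescriptions in 2012 are excluded from analysis". The synopsis extends the window up to treatment start: "Patients with previous prescription of opioid medication or non-opioid medication between 01.01.2012 and index treatment will be excluded". Time zero is set in Section 9.2.1: "Index treatment is defined as the date of first opioid or non-opioid treatment prescription between 1st January 2013 and 31st December 2017".

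On insurance cover, Section 9.2 has one sentence: "Source population of the study are patients covered by the German Health Claims database over 2012-2017 years". The same section lists "date of insurance start and end" among the available fields, but no eligibility rule uses them. Section 9.1 names change of insurance as a reason for losing a patient. It says nothing about people who arrive by changing insurer.

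For both cohorts Section 9.2.2.1 asks that "At least one diagnoses must be between 1 January 2012 and index treatment". Its further requirement of three diagnosis quarters is worded differently for each cohort, and differently again in the synopsis.

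**The concern.** All versions of the washout test for recorded prescriptions. A person who was not insured with a participating fund in 2012 has none, whatever that person was taking. The protocol's own facts make entry from outside plausible: 69 of about 120 statutory insurers contribute, the full database holds about 10% of the statutory insured, and the privately insured are absent.

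If established users enter as new users, three things suffer. Their time zero is not the start of treatment, so they have already survived an early period that true new users are followed through. Their baseline is cut short, so the comorbidity index and propensity score rest on incomplete records. Misuse or addiction diagnoses that predate entry may be missed or dated as new. The primary endpoint is death from any cause, so both survivor selection and hidden illness bear on the main comparison.

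**Working it through.** The protocol gives no figure on this point to reproduce. The check is a reading of the rules, followed by an illustration on assumed inputs.

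**1. How much insured time before index does each rule imply?**

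| Rule | Three diagnosis quarters must fall | Insured look-back implied |
|---|---|---|
| 9.2.2.1, Cohort A bullet | anywhere in the study period, with one diagnosis before index | no minimum length |
| 9.2.2.1, Cohort B bullet | in 2012 | cover in at least three quarters of 2012 |
| 9.2.2.1, closing sentence on all inclusion diagnoses (leads to Table 9-2, both cohorts) | within the study period, with a diagnosis before index | no minimum length, either cohort |
| Synopsis | between 1 January 2012 and the first opioid claim | three quarters with diagnoses, but not necessarily in 2012 |

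Only the Cohort B bullet forces cover in 2012, and the closing sentence of the same section does not agree with it.

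**2. Trace one case under 9.2.2.1.** Take a person already on an opioid who joins a participating insurer in 2014.
- Prescriptions in 2012: none recorded, so the washout is passed.
- Prescriptions from 1 January 2012 to index: none recorded, because index is the first one seen.
- Pain diagnosis: one coded after joining and before the first recorded claim is enough. The three quarters can be completed later.
- Opioid prescriptions in at least three consecutive quarters: met by continuing treatment.

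The person can enter Cohort A with time zero in 2014. Under the synopsis rule the same person would need three diagnosis quarters before the first recorded claim. A continuous user, who normally renews soon after joining, would rarely manage that.

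**3. Other safeguards that use the same window.** In Section 9.2.2.2 the cancer-treatment exclusion looks from 1 January 2012 to index, and the palliative-care exclusion looks before index. The Charlson index is taken at baseline (9.3.2). The one listed sensitivity analysis (9.8.2) removes cancer diagnoses before index. For a late joiner, none of these can see anything before the joining date.

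**4. Illustration of size.** Let *j* be the yearly share of insured persons who newly join and *D* the mean duration of long-term opioid use in years. Neither is in the protocol. In a steady state with incidence *i*, prevalence is *iD*. Each year then brings *i* true new users and *j·iD* established users who join, so the established share of apparent new users is

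f = jD / (1 + jD)

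- j = 0.5%, D = 1: 0.005/1.005 = 0.5%
- j = 1%, D = 2: 0.02/1.02 = 2.0%
- j = 2%, D = 3: 0.06/1.06 = 5.7%
- j = 5%, D = 5: 0.25/1.25 = 20%

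This assumes that joiners use opioids as often as the insured population does. It ignores the pre-index diagnosis, which would remove some of them.

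For the hazard ratio, assume a true new-user ratio of 2.0. Section 9.3.1 expects 100 to 200 deaths per 10,000 person-years; giving the two ends to the two arms is an assumption. Let established users have *k* times the new-user hazard. The crude mixed ratio is 2.0 × [(1 − f) + f·k]:

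- f = 2%: 1.98 (k = 0.5) to 2.02 (k = 1.5)
- f = 20%: 1.80 (k = 0.5) to 2.20 (k = 1.5)

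**The case against.** The strongest reply is that the protocol presupposes observation from 2012. Section 9.2.1 starts the baseline period on 1 January 2012, and the source-population sentence can be read as cover from 2012 until death or exit, which fits the censoring rules. Section 9.1 also calls the database complete and longitudinal. This shows a likely intention, but none of it is an eligibility criterion. A programmer extracting the cohort from Section 9.2.2 would apply no cover check. Figure 2 and the study-period figure could not be read for this review, so a condition there cannot be ruled out; the text that Figure 2 is said to repeat has none.

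The second reply is the synopsis rule, which would screen out most continuous users. That is correct. But it conflicts with Section 9.2.2.1 for Cohort A, and it still does not ask for cover in 2012. It limits the concern and does not remove it.

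A reader might infer three stronger points that the document does not support:
- *That only the opioid arm is contaminated.* This holds only if the 2012 wording in the Cohort B bullet governs. Under the closing sentence of Section 9.2.2.1, Cohort B is open too.
- *That the source-population sentence, read strictly, removes everyone who dies.* The reading of cover until death or exit is available, and Sections 9.1, 9.2.1 and 9.4.2.1 expressly follow patients to death or last record. The sentence is ambiguous, and that is all that can be said against it.
- *That a particular share of Cohort A is misclassified.* The count of insurers says nothing about how many people change, and no transfer rate or duration of use is given.

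**Conclusion.** The point stands as a gap in a stated rule. As written, the washout treats absence of claims as absence of treatment, and Section 9.2.2.1 lets an established user who joins late qualify for Cohort A. The exact word is can: entry still needs a recorded pain diagnosis before the first recorded claim, and the synopsis rule, if it governs, would stop most cases.

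Neither the size nor the net direction of the bias can be derived from the protocol. Survivor selection would make opioids look safer, while unrecorded illness can make them look worse. The range of 0.5% to 20% rests wholly on assumed joining rates and durations. In the crude mixture above the hazard ratio moves little at small shares and by up to 0.2 either way at the upper end. Because the bias cannot be sized and the remedy is cheap, the rule should be corrected before extraction. The document does not show that the primary result would be overturned.

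**What to change.** Add to Section 9.2.2, in identical words for both cohorts: continuously insured in the database from 1 January 2012 to index treatment, checked with the insurance start and end dates, with no cover condition after index. The date matches the start of the protocol's own baseline period.

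Reword the source-population sentence in Section 9.2 so that people who die or leave after index are clearly kept. Reconcile the diagnosis-quarter rules in the synopsis, the two cohort bullets and the closing sentence of Section 9.2.2.1, so that both cohorts face one rule.

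The programming cost is small, because the field exists. The cost in patients is everyone who joined after 1 January 2012, including some with several clean insured years; an index date at the end of 2017 would demand nearly six years of unbroken cover. A shorter fixed look-back, such as at least 12 insured and claim-free months before index, would lose fewer people. It would require the washout to be anchored to index instead of calendar year 2012. Either version works if it is stated and applied equally to both cohorts.

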7.1 Diseases and Therapeutic Area

Chronic non-cancer pain describes back, musculoskeletal, abdominal, headache and other neurologic pain without an evidence of cancer¹.

¹ Dowell et al., 2016

Today, chronic pain is one of major health care problems in Europe. For instance, a large telephone survey in 15 European countries and Israel showed that chronic non-cancer pain of moderate to severe intensity has a prevalence of 19 % affecting the quality of patient's social and working lives². Common treatment of moderate to severe chronic pain includes opioids, analgesic anticonvulsants³ and low-dose cyclic antidepressants⁴. Analgesic anticonvulsants and low-dose cyclic antidepressants can have serious adverse effects⁵. But also the tendency of increased prescriptions of opioid analgesics leads to a discussion about potential harms of this medication⁶.

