9.4.2.2 Secondary endpoints

Secondary endpoints are following:

- **Hospitalization due to any course.** Hospitalization will be assessed via the number of hospitalisations (calculated by counting the number of discharge dates (KH_Fall. Entlassungsdatum) in the year of interest, hospitalization rate, and length of stay in the hospital (KH_Fall. Verweildauer). The rate of hospitalization will be estimated as the number of patients with at least one hospitalization during the follow-up period divided by person-time of follow-up, censoring at time of death, last known record for the patient in the database, or 31st December 2017 (end of latest data cut), whichever is earlier.
- **Intensive care unit (ICU-stay)** stay is defined as patient's stay based on specialty of department in hospital (KH_OPS.Fachabteilung = 3600).
- **Hospitalization with to misuse or addiction.** The hospitalization with misuse or addiction will be analysed, if principal (main) diagnosis at discharge date between January 1st 2013 and December 31st 2017 contains at least one ICD-10 diagnosis of misuse/addiction: F10* or F11* or F13* or F19* or T40* (see also Appendix B in **Fehler! Verweisquelle konnte nicht gefunden werden.**).
- **Hospital admission diagnoses.** We report the hospital admission diagnoses based on ICD-10 codes between January 1st 2013 and December 31st 2017.
- **Coding of procedures in hospitals** that indicate number of patients that were hospitalized with severe diseases such as cardiovascular

diseases will be assessed via OPS-Codes provided in Appendix B as an excelsheet.

- **Coding of a misuse or addiction diagnosis in the outpatient sector** will be assessed via number of codings of misuse/addiction (ICD Codes = F10* or F11* or F13* or F19* or T40*) in outpatient sector by general practitioner or a specialist (e.g. psychiatrist), as ensured diagnosis (Diagnosesicherheit='G'). Additionally, the number of patients with a least one coding of ICD 10 codes of an ensured misuse/addiction in outpatient sector by general practitioner or a specialist (e.g. psychiatrist) will be assessed.
- **Sick leave** will be assessed as an absolute number and relative frequencies of patients with an attest of inability to work (patients with attest of inability to work as a percentage of all patients) in 2013-2017 and number of days being off work.
- **Hospital deaths** will be assessed via reason of discharge = death (Entlassgrund = Tod)

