9.8.2 Sensitivity analysis

The following main sensitivity analysis will be conducted:

Sensitivity analysis
No cancer patients: Exclude all patients with at least one C00 – C96 diagnosis before index date

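### The cancer exclusion depends on a same-quarter treatment code, so patients with coded cancer before index can stay in the primary noncancer-pain mortality comparison

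*Protocol*

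**What the plan says.** The operative rule is in Protocol section 9.2.2.2: "Cancer patients will be excluded if the cancer diagnosis is accompanied by at least one of the following treatments in the same quarter". The text goes on to name "radiation therapy or chemotherapy all defined by the codes in Table 9-3". The table pairs C00-C97 with the condition "Plus at least one the following in the same quarter" and lists ICD-10 codes Z51.0, Z51.1 and Z51.5, and OPS codes for chemotherapy, radiation and palliative care.

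On timing and source, the section says: "Diagnoses will be assessed via ICD-10 diagnoses during the inclusion period from 1 January 2012 until index treatment". It adds that main and secondary hospital diagnoses count, and does not mention outpatient diagnoses. A separate bullet excludes any palliative care coded before index, with no cancer code or same-quarter match required.

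Three other places bear on the rule:

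- Section 7.1 describes chronic noncancer pain as back, musculoskeletal, abdominal, headache and "other neurologic pain without an evidence of cancer".
- Section 9.8.2 plans one sensitivity analysis: "Exclude all patients with at least one C00 – C96 diagnosis before index date".
- The synopsis places the exclusion for cancer treatment after index treatment, not before it.

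**The concern.** The study is about noncancer pain and its primary endpoint is death from any cause. Cancer raises the risk of death and may also raise the chance of receiving an opioid, so retained cancer patients are a plausible confounder of exactly this comparison. The rule that would remove them appears only as a sensitivity analysis.

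The rule is also an unreliable filter for active cancer, because it needs a treatment code from a short list in one particular quarter. Cancer that is untreated, treated by surgery, or treated with dispensed drugs need not produce such a code. What is at stake is whether the headline hazard ratio describes the population named in the objective.

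**Working it through.** The protocol gives no residual cancer share, event count or power figure, so there is no stated number to reproduce. The check has three parts.

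**1. Which cancer patients can pass the rule**

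| Source of information | In the database (section 9.2) | Used in Table 9-3 |
|---|---|---|
| Hospital diagnoses, ICD-10 | yes | yes |
| Outpatient diagnoses, ICD-10 | yes | not stated |
| Procedures, OPS | yes | yes |
| Outpatient procedures, EBM | yes | no |
| Dispensed drugs, ATC | yes | no |

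Section 9.4.2.2 introduces OPS codes for procedures in hospitals ("diseases will be assessed via OPS-Codes"). Section 9.2 records outpatient care separately, as "procedures performed (EBM codes, e.g. laboratory tests, radiology, echocardiography) and date of procedure". Outpatient treatment can therefore trigger the exclusion only through a Z51 code, and only if outpatient diagnoses count.

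The protocol itself expects cancer patients in the main cohort: Table 9-4 scores solid cancer 2 and metastatic cancer 6, and section 9.8.2 sets out to remove them.

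**2. What the planned adjustment does**

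The Charlson index enters the Cox model as one summed baseline score (section 9.3.2). Solid cancer scores 2, as do complicated diabetes, hemiplegia and kidney disease. Complicated diabetes in Table 9-4 includes the .4 diabetes codes, which together with G63.3 are an inclusion diagnosis. A patient with diabetic neuropathy and a patient with solid cancer thus receive the same points. C80* is listed as both solid and metastatic. Section 9.3.1 names sleep apnoea, depression and other comorbidities for the propensity score; cancer is not named there, and Appendix A is not at hand.

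**3. How large the effect could be**

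The illustration is crude, before matching and adjustment. Section 9.3.1 expects 100 to 200 deaths per 10,000 person-years; take 150 for noncancer patients in both cohorts, with no true treatment effect. Cancer shares and cancer mortality are assumptions.

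Cohort rate = (1 − share) × 150 + share × cancer rate.

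- Share 2% in A and 0.5% in B, cancer rate 2,000:
  - A: 0.98 × 150 + 0.02 × 2,000 = 187.0
  - B: 0.995 × 150 + 0.005 × 2,000 = 159.25
  - ratio 187.0/159.25 = 1.17
- Share 0.5% in A and 0.25% in B, cancer rate 1,000:
  - A: 0.995 × 150 + 0.005 × 1,000 = 154.25
  - B: 0.9975 × 150 + 0.0025 × 1,000 = 152.125
  - ratio 154.25/152.125 = 1.01

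In general, with shares a and b in cohorts A and B, and R the ratio of cancer to noncancer mortality, the spurious ratio is [1 + a(R − 1)]/[1 + b(R − 1)].

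| Share in A, share in B | R = 3 | R = 5 | R = 10 |
|---|---|---|---|
| 2%, 2% | 1.00 | 1.00 | 1.00 |
| 4%, 2% | 1.04 | 1.07 | 1.15 |
| 10%, 5% | 1.09 | 1.17 | 1.31 |

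The distortion can also run the other way. Suppose the true ratio is 2.0 in noncancer patients, treatment has no effect in cancer patients, and 5% of each cohort has cancer. The crude ratio is [2 × 0.95 + 0.05R]/[0.95 + 0.05R]:

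- R = 5: 2.15/1.20 = 1.79
- R = 10: 2.40/1.45 = 1.66

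**The case against.** The strongest reply is that this is a deliberate and largely covered design choice. Section 7.1 is background, and section 9.2 defines the study population as those who meet the eligibility criteria. A past cancer code does not turn back pain into cancer pain. The any-cancer exclusion is already planned as a sensitivity analysis, and cancer enters the Charlson score. Palliative care before index is excluded separately, which removes some of the patients at highest risk. The requirements of no study medication in 2012 and prescriptions over at least three quarters also limit who can be retained. The size of any bias is assumed.

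Much of this stands, and it rules out three stronger readings that a reader might infer:

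- That every cancer patient without a same-quarter treatment code is kept. The separate palliative-care exclusion contradicts this.
- That all active cancer managed outside hospital stays in. Z51.0 and Z51.1 are diagnosis codes and could identify outpatient treatment if outpatient diagnoses count. Section 9.2.2.2 names only hospital diagnoses but does not rule out others, and section 9.5 foresees ensured outpatient diagnoses. That OPS codes are confined to hospital care is also an inference from section 9.4.2.2; section 9.3.1 uses them with no such limit stated.
- That the hazard ratio will be inflated. The documents give no cancer shares, so neither direction nor size is established.

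The reply does not settle the main point. Excluding only active cancer could be a sound design, but this code list does not identify active cancer reliably, and a sensitivity analysis does not change what the headline estimate describes.

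**Conclusion.** The concern holds in a limited form. Patients with coded cancer before index, including metastatic cancer, can be in the primary cohort when no Table 9-3 code falls in the same quarter and no palliative care is coded before index. This follows from the wording and code list and needs no assumption. Whether it matters numerically rests on the unknown share of such patients in each cohort and on their mortality. The two main scenarios give about 1.01 to 1.17 with no true effect, and the wider grid runs from 1.00 to 1.31. Matching and the Charlson term would remove part of this, though one summed score is a coarse adjustment for cancer. The rule should be changed because it shapes the primary result and the alternative is already written into the protocol.

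**What to change.** - Make the section 9.8.2 rule primary: exclude any patient with a C00-C97 diagnosis, hospital or ensured outpatient, from 01.01.2012 to index.
- Keep the same-quarter treatment rule as the sensitivity analysis.
- Correct C96 in section 9.8.2 so that it agrees with C97 in Table 9-3.
- Reconcile the synopsis (exclusion after index) with section 9.2.2.2 (until index).
- In the retained treatment rule, state which diagnosis sources count and whether palliative care is a qualifying treatment; the text and Table 9-3 differ on this. Consider adding EBM and ATC codes.

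No new data are needed. The primary cohort becomes somewhat smaller, by an amount the protocol does not allow one to estimate, and its result no longer extends to cancer survivors. They remain in the sensitivity analysis.
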